### **13.10.2 Computing Environment**

Efficacy and safety analyses will be performed using SAS for windows, Version 9.2 or higher (SAS Institute Inc., Cary, NC, USA).

PK analyses will be performed using Phoenix WinNonlin version 6.3 or higher (Pharsight, Cary, NC, USA).

---

## 14 DIRECT ACCESS TO SOURCE DATA/DOCUMENTS

### 14.1 Study Monitoring

A representative of the Sponsor or designee may visit the investigational study site to:

- Determine the adequacy of the facilities and equipment
- Discuss with the Investigators and other personnel their responsibilities with regard to protocol adherence, and the responsibilities of the Sponsor or its representatives. This will be documented in a Clinical Study Agreement between the Sponsor and the Investigator.

During the study, a representative of the Sponsor or designee will have regular contact with the investigational site, for the following:

- Provide information and support to the Investigators
- Confirm that facilities and equipment remain acceptable
- Confirm that all patients have been properly consented
- Confirm drug accountability
- Confirm that the investigational team is adhering to the protocol, that data are being accurately recorded in the CRFs/eCRFs, and that study drug accountability checks are being performed
- Perform source data verification. This includes a comparison of the data in the CRFs/eCRFs with the patient's medical records at the hospital or practice, and other records relevant to the study. This will require direct access to all original records for each patient (eg, clinic charts).
- Record and report any protocol deviations not previously sent to the Sponsor.
- Confirm AEs and SAEs have been properly documented on CRFs/eCRFs and confirm any SAEs have been forwarded to the Sponsor and those SAEs that met criteria for reporting have been forwarded to the IRB.

The monitor will be available between visits if the Investigators or other staff needs information or advice.

### 14.2 Audits and Inspections

Authorized representatives of the Sponsor, a regulatory authority, an IEC or an IRB may visit the site to perform audits or inspections, including source data verification. The purpose of an audit or inspection by the Sponsor is to systematically and independently examine all study-related activities and documents to determine whether these activities were conducted, and data were recorded, analyzed, and accurately reported according to the protocol, Good Clinical Practice (GCP) guidelines of the International Council for Harmonisation (ICH), and any applicable regulatory requirements. The Investigator should contact the Sponsor immediately if contacted by a regulatory agency about an inspection.

### 14.3 Institutional Review Board

The PI must obtain IRB/IEC approval for the investigation. All IRB/IEC approvals, including initial and continued review, and all materials approved by the IRB/IEC for this study including the patient consent form and recruitment materials must be maintained by the Investigator and made available for inspection.

## 15 QUALITY CONTROL AND QUALITY ASSURANCE

To ensure compliance with GCP and all applicable regulatory requirements, the Sponsor or designee may conduct quality assurance audits ([Section 14.2](#)).

## 16 ETHICS

This study will be performed in accordance with ethical principles that have their origin in the Declaration of Helsinki and are consistent with ICH GCP guidelines.

Investigators and other study personnel must comply with all instructions and regulations specified in this protocol and applicable ICH GCP guidelines and must conduct this study in accordance with all local, federal, and regulatory agency regulations.

In accordance to ICH guidelines, pediatric participation in these studies should occur in qualified pediatric centers, with personnel who are properly trained and experienced in studying the pediatric population and in evaluating and managing potential pediatric AEs. Site personnel should be knowledgeable and skilled in dealing with the pediatric population and its age-appropriate needs and be encouraged to use measures that minimize discomfort of procedures (e.g., topical anesthesia to place IV catheters, use of indwelling catheters instead of repeated venipunctures for blood sampling, and collection of some protocol-specified blood samples when routine clinical samples are obtained).

### 16.1 Ethics Review

The final study protocol, including the final version of the ICF, must be approved or given a favorable opinion in writing by an IRB or IEC as appropriate. The Investigator must submit written approval to the Sponsor before he or she can enroll any patient into the study.

No modifications to the protocol should be made without the approval of both the Investigator and the Sponsor. Changes that significantly affect patient safety, the scope of investigation, or the scientific validity of the study will require IRB/IEC notification prior to implementation, except where the modification is necessary to eliminate an apparent immediate hazard to patients. Any deviations from protocol must be fully documented. The PI is responsible for informing the IRB or IEC of any amendment to the protocol in accordance with local requirements. In addition, the IRB or IEC must approve all advertising used to recruit patients for the study. The protocol must be re-approved by the IRB or IEC upon receipt of amendments and annually, as local regulations require.

The PI is also responsible for providing the IRB with reports of any reportable serious adverse drug reactions from any other study conducted with the study drug. The Sponsor will provide this information to the PI.

Progress reports and notifications of serious adverse drug reactions will be provided to the IRB or IEC according to local regulations and guidelines.

### 16.2 Data Monitoring Committee Review

An independent DMC will be appointed by the Sponsor [REDACTED] who have no direct relationship with the study.

Prior to each scheduled dose escalation, the SRC chair will convene the DMC to review laboratory and clinical data in conjunction with the SRC to determine if dose escalation is appropriate ([Section 3.4](#)).

Final decisions regarding the conduct of the study will be made by the Sponsor after consultation with the DMC. All appropriate regulatory authorities and ECs will be notified of any significant action.

The DMC may be asked to provide medical and ethical guidance related to the conduct of the study as described above. The DMC will review study information as outlined in the DMC charter, which is maintained separately from the study protocol.

Each member of the DMC will be required to sign a contract agreement, which includes a confidentiality and financial disclosure statement, assuring no conflicts of interest as a condition for membership on the board.

### **16.3 Written Informed Consent**

The PIs at each center will ensure that the patient's parent or legal guardian is given full and adequate oral and written information about the nature, purpose, possible risk and benefit of the study. The patient's parent or legal guardian must also be notified that they are free to discontinue their child from the study at any time. The parent or legal guardian should be given the opportunity to ask questions and allowed time to consider the information provided.

The signed and dated ICF must be obtained before conducting any study procedures.

The PIs must maintain the original, signed ICF. A copy of the signed ICF must be given to the patient's parent or legal guardian.

Should new information become available during the conduct of the study that might impact parent or legal guardian willingness to continue participation in the study, the parent or legal guardian will be notified in a timely manner about the new information and asked to sign a new ICF.

### **16.4 Patient Data Protection**

Prior to the performance of any study-related procedures, the patient's parent or legal guardian must authorize the release and use of protected health information as required by local, federal and regulatory agency law.

CRFs/eCRFs will be completed at the site either on paper or in the electronic data capture system. Copies of pertinent records in connection with the study, including patient charts and laboratory data, will be made available to the Sponsor or designee on request in a timely manner throughout the course of the study, with due precaution toward protecting patient privacy.

## 17 DATA HANDLING AND RECORDKEEPING

### 17.1 Inspection of Records

[figure not shown]
The Sponsor or designee will be allowed to conduct site visits to the investigation facilities for the purpose of monitoring any aspect of the study. The Investigator agrees to allow the monitor to inspect the drug storage area, study drug stocks, drug accountability records, patient charts and study source documents, and other records relative to study conduct.

### 17.2 Retention of Records

The PI must maintain all documentation relating to the study in accordance with local retention requirements, or for a period of 2 years after the last marketing application approval, or, if not approved, 2 years following the discontinuance of the test article for investigation. If it becomes necessary for the Sponsor or the regulatory authority to review any documentation relating to the study, the Investigator must permit access to such records. No records may be destroyed without Sponsor written approval.

### 17.3 Retention of Biological Samples

If a patient's parent or legal guardian has/have provided consent for long-term storage of biological samples, and if permitted by local regulatory authorities, any remaining sample will be stored at a central location for a maximum of 15 years after the last patient's last study visit or longer, if requested by regulatory authorities.

The samples and data for biochemical analysis in this study will be single coded. The link between the patient enrollment number and the biochemical results will be maintained and stored in a secure environment, with restricted access. The link will be used to identify the relevant samples for analysis, facilitate correlation of biochemical results with clinical data, allow regulatory audit, and to trace samples for destruction in the case of withdrawal of consent when the patient or consenting guardian has requested disposal/destruction of collected samples not yet analyzed.

If a patient's parent or legal guardian withdraws consent to the use of donated biological samples, the samples will be destroyed, and the action will be documented. If samples are already analyzed, the Sponsor is not obliged to destroy the results of this research.

---

**17.4 Data Privacy**

The Sponsor will make every effort to protect patient privacy. For all study data collection, patients will be identified by a unique patient number and date of birth in regions where permitted. The results from this study may be presented at meetings or in articles. However, patient name or initials that could identify a patient will not be used in any such meetings or articles.

**18 PUBLICATION POLICY**

The full terms for publication are outlined in the Clinical Study Agreement, Statement of Agreement, or Master Clinical Study Agreement. Publication terms permit publication only after publication of multicenter results and require that any data to be submitted for publication including abstract submissions or presentations, be submitted to the Sponsor for review at least 30 days prior to submission.

**20 APPENDICES**

- [Appendix A](#) Blood Sampling Volumes (European Commission 2008; European Medicines Agency (EMA) 2009)
- [Appendix B](#) Blood Sampling Volumes Table (Screening Through Month 6)
- [Appendix C](#) Blood Sampling Volumes Table (Extension Period and Safety Follow- Up Visit)
- [Appendix D](#) Blood Sampling Volumes for Unscheduled Dose Adjustment

**Appendix A. BLOOD SAMPLING VOLUMES**

[REDACTED] In particular, an alternative blood sampling schedule for infants weighing less than 10 kg, for whom less blood volume should be collected, must be used [REDACTED].

The following procedures for blood collection should be adhered to:

1. Number of attempts: The number of attempts for sampling blood is limited to 3 times per day. This means that after 3 punctures for collection of blood have been performed and no or insufficient blood could be collected, no other puncture will be done on the same day.

Volume of blood samples: Per study patient, the study-related blood loss (including any losses in the collection procedure) should not exceed 3% of the total blood volume during a period of 4 weeks and should not exceed 1% at any single time. The total volume of blood is estimated at 80 to 90 mL/kg body weight. Three percent (3%) is 2.4 mL blood per kg of body weight. If an Investigator decides to deviate from these limits, the deviation must be fully documented, and the Investigator should provide justification for the deviation. If the required blood volume cannot be obtained due to the above- mentioned safety limits, priority will be given to safety-relevant investigations.

Eutectic mixture of local anesthetics (EMLA) cream/plaster: To minimize the possible pain and discomfort due to the collection of blood, the Investigator should apply an EMLA cream/plaster at the site of puncture.

**Appendix B. BLOOD SAMPLING VOLUMES TABLE (SCREENING THROUGH MONTH 6)**

**Table 10: Blood Sampling Volumes (Screening Through Month 6)**

		Study Day
Sample	Marker or Specific Time	
Genotype (if not previously done)		
Serum Chemistry		
Hematology		
Coagulation		
Biochemical PD Markers	██████████ e	
██████████		
ORGN001 levels (PK)	Preinfusion	
	EOI	
	0.5 hrs. after the EOI	
	1 hr. after the EOI	
	2 hrs. after the EOI	
	3 hrs. after the EOI	
	4 hrs. after the EOI	
	5 hrs. after the EOI	
	24 hrs. after the EOI 	
██████████		

Note regarding blood samples: The total blood volume will not exceed the amount considered acceptable for the patient’s clinical condition and the institution’s guidelines ██████████. If an Investigator decides to deviate from these limits, the deviation must be fully documented, and the

Investigator should provide justification for the deviation.

 An optional venous blood sample may be collected at 24 hours after the EOI for PK and PD assessments.

Abbreviations: EOI = end of infusion; [redacted] mL = milliliters; PD = pharmacodynamic; PK = pharmacokinetics; SSC = S-sulfocysteine.

### Appendix C. --BLOOD SAMPLING VOLUMES (EXTENSION PERIOD AND SAFETY FOLLOW-UP VISIT)

**Table 11: Sample Volume Collection During the Extension Period and Safety Follow--Up Visit**

Assessment	Extension Period	
Month		
Visit Window (Days)		
Serum chemistry		
Serum hematology		
PD sampling, predose blood 		
PD sampling, blood 		
ORGN001 levels (PK) 		

Note regarding blood samples: The total blood volume will not exceed the amount considered acceptable for the patient’s clinical condition and the institution’s guidelines [REDACTED]. If an Investigator decides to deviate from these limits, the deviation must be fully documented, and the Investigator should provide justification for the deviation.

[REDACTED]

 Collect venous blood samples [REDACTED] for SSC, [REDACTED] biomarker analysis.

 Pharmacokinetics will be collected at 1 visit between Month 7 and the last month of the Extension Period at the EOI and 4 hours post EOI.

Abbreviations: EOI = end of infusion; mL = milliliters; PD = pharmacodynamic; PK = pharmacokinetics; SSC = S-sulfocysteine.

**Appendix D. BLOOD SAMPLING VOLUMES FOR UNSCHEDULED DOSE ADJUSTMENT**

**Table 12: Sample Volume Collection for an Unscheduled Dose Adjustment**

Assessment	Specific Time	First Day Adjusted Dose is Administered	Follow-Up Visit
Serum chemistry	Any time during study visit	[REDACTED]	[REDACTED]
Serum hematology			
PD sampling, blood	3 to 4 hours after the EOI		
PK sampling	EOI		
PK sampling	3 to 4 hours after the EOI		

Note regarding blood samples: The total blood volume will not exceed the amount considered acceptable for the patient’s clinical condition and the institution’s guidelines [REDACTED]. If an Investigator decides to deviate from these limits, the deviation must be fully documented, and the Investigator should provide justification for the deviation. [REDACTED]

Abbreviations: EOI = end of infusion; meds = medications; PD = pharmacodynamics; PK= pharmacokinetics.

2. LIST OF ABBREVIATIONS AND DEFINITIONS OF TERMS

The following abbreviations and acronyms are used in this SAP.

Table 1: Abbreviations and Acronyms

Abbreviation or Acronym	Explanation
AE	Adverse event
ATC	Anatomical therapeutic chemical
AUC	Area under the plasma concentration-time curve
Bayley-III	Bayley Scales of Infant Development-Third Edition
BMI	Body mass index
BP	Blood pressure
BQL	Below quantification level
CDC	Centers for Disease Control and Prevention
C _{max}	Maximum observed plasma concentration
CSR	Clinical Study Report
CT	Computed tomography
DMC	Data Monitoring Committee
DQ	Developmental quotient
EEG	Electroencephalogram
FAS	Full Analysis Set
GMFCS-E&R	Gross Motor Function Classification System-Expanded and Revised
HR	Heart rate
LLOQ	Lower limit of quantification
MedDRA	Medical Dictionary for Regulatory Activities
MoCD	Molybdenum Cofactor Deficiency Type A
MRI	Magnetic resonance imaging
NCI	National Cancer Institute
PD	Pharmacodynamics
PK	Pharmacokinetics
PI	Principal Investigator
PT	Preferred term
PTAE	Pre-treatment adverse events
rcPMP	Recombinant Escherichia coli -derived Cyclic Pyranopterin Monophosphate
RBC	Red blood cell
RR	Respiratory rate
SAE	Serious adverse event
SAS	Statistical Analysis Software
SAP	Statistical Analysis Plan
SD	Standard deviation
SOC	System organ class
SRC	Safety Review Committee
█	█

Abbreviation or Acronym	Explanation
$t_{1/2}$	Terminal half-life
TEAEs	Treatment-emergent adverse events
t_{max}	Time to maximum observed plasma concentration
WHO	World Health Organization
WPPSI	Wechsler Preschool and Primary Scale of Intelligence

3. DESCRIPTION OF THE PROTOCOL

Protocol Number: ALXN1101-MCD- [REDACTED]

[REDACTED]		
[REDACTED]	[REDACTED]	[REDACTED]
[REDACTED]	[REDACTED]	[REDACTED]
[REDACTED]	[REDACTED]	[REDACTED]
[REDACTED]	[REDACTED]	[REDACTED]
[REDACTED]	[REDACTED]	[REDACTED]

		[REDACTED]
[REDACTED]	[REDACTED]	[REDACTED]
[REDACTED]	[REDACTED]	[REDACTED]

Title: A Phase 2, Multicenter, Multinational, Open-label, Dose-Escalation Study to Evaluate the Safety Efficacy of ORGN001 (formerly ALXN001) in Pediatric Patients with Molybdenum Cofactor Deficiency (MoCD) Type A Currently Treated with Recombinant *Escherichia coli*-derived Cyclic Pyranopterin Monophosphate (rcPMP).

This Phase 2, multinational, multicenter, open-label, dose-escalation study is designed to evaluate the safety and efficacy of ORGN001 (formerly ALXN1101) administered to infants and children with MoCD Type A currently treated with rcPMP. Eligible subjects will be identified through [REDACTED] use with rcPMP. This study will include a screening period (Days -21 to Day -1), a 6-month study period that includes escalating doses of ORGN001 after the first 2 months of treatment with ORGN001 (Day 1 [first dose of study drug] to Day 180), and a [REDACTED] extension period (after Day 180).

Screening evaluations will be performed at any time during the screening period before the first dose of ORGN001. Enrolled subjects will attend at least 2 study visits in order for baseline data to be obtained. During the screening period, subjects will continue to receive daily IV infusions of current rcPMP treatment. During the 6-month initial treatment period, starting on Day 1, subjects will begin IV infusions of ORGN001 at the same dose as their current dose of rcPMP approximately 24 hours after their last treatment with rcPMP. No further treatments with rcPMP will be allowed during the study. Subjects [REDACTED] will continue to receive daily infusions of ORGN001 at home [REDACTED] and will attend multiple study visits for safety, efficacy, pharmacodynamic (PD), and pharmacokinetic (PK) assessments through Month 6 of the initial treatment period and [REDACTED] the extension period. After the first 2 months of treatment with ORGN001, if the subject's clinical, PK, and safety assessments permit (including the absence of signs and symptoms of drug-related toxicity), dosing with ORGN001 will increase every month [REDACTED] based on the subject's clinical response, safety labs, and when appropriate, exposure data. [REDACTED] [REDACTED]. After the 6-month study period, subjects will enter the [REDACTED] extension period and continue to receive uninterrupted daily dosing of ORGN001 at their final tolerated dose based on the dose escalation. After dose escalation is complete, the subject can be returned to the prior dose based on the subject's clinical status at the discretion of the treating physician after consultation with the Safety Review Committee (SRC). Subjects who prematurely discontinue from the study will attend a safety follow-up visit [REDACTED] and return to the care of their treating physician.

The study objectives are as follows:

Primary Objective:

The primary objective of this clinical study is to evaluate the safety of ORGN001.

Secondary Objectives:

The secondary objectives of this clinical study are to:

- Characterize the PK of increasing doses of ORGN001
- Evaluate the effect of ORGN001 on urine and blood [REDACTED] levels
- Evaluate the effect of ORGN001 on neurologic, motor, and cognitive functions
- Evaluate the effect of ORGN001 on central nervous system structure
- Evaluate the long-term safety of ORGN001

[REDACTED]
[REDACTED]
[REDACTED]
[REDACTED]
Additional information about the study can be found in the protocol.

Results from this study will be summarized in a clinical study report (CSR).

3.1. Changes from Analyses Specified in the Protocol

Not applicable.

[REDACTED]

4. DEFINITIONS

4.1. Efficacy

There is no pre-specified primary efficacy endpoint in this study. The secondary efficacy endpoints at all key study timepoints include:

- Change from baseline in urine and blood [REDACTED] levels
- Change from baseline in clinical findings from neurologic examination
- Change from baseline in age-appropriate motor and cognitive assessments (Bayley Scales of Infant Development-Third Edition [Bayley-III], The expanded and revised Gross Motor Function Classification System [GMFCS-E&R], Wechsler Preschool and Primary Scale of Intelligence [WPPSI])
- Change from baseline in seizure frequency
- Change from baseline in neuroimaging
- Changes in growth parameters (body weight, body length, head circumference)
- Change from baseline in feeding patterns

4.1.1. Neurologic Examinations

Neurologic examination includes, but is not limited to, assessment of mental status, cranial nerves, motor strength and tone, sensory examination, deep tendon reflexes and primitive reflexes, if present.

4.1.2. Bayley Scales of Infant and Toddler Development-Third Edition

The Bayley-III will be administered to assess changes in gross motor, language, fine motor, and cognitive development. The Bayley-III will be administered to children under 3 years of age and to subjects with severe developmental delay for whom the WPPSI is not an appropriate assessment.

The Bayley-III is a standardized and norm-referenced instrument that assesses the developmental functioning of infants and children 1 month to 42 months of age. The Bayley-III consists of 3 administered scales: the Cognitive Scale, the Language Scale (administered only to native English speakers in English-speaking countries and includes the Receptive Communication and Expressive Communication subtests), and the Motor Scale (including the Fine Motor and Gross Motor subtests).

From the raw scores, scaled scores can be calculated for the cognitive scale and the 2 combined language scales and motor scales.

These scores can then be used to determine composite scores, percentile ranks and confidence intervals, development age equivalents, and growth scores.

Scaled scores range from 1 to 19, with a mean of 10 and a standard deviation (SD) of 3. The composite score is scaled to a metric with a mean of 100, a SD of 15, and range from 40 to 160.

Percentile ranks indicates percentage of individuals in standardization sample, at a given age, who obtained scores less than or equal to a given scaled score or composite score. Percentile ranks range from 1 to 99, with 50 as the mean and median.

Developmental age equivalents represent the average age in months at which a given total raw score is typical.

The developmental age equivalent raw score can be used to calculate the developmental quotient (DQ). The DQ is the age equivalent score divided by chronological age.

- $DQ = \text{age equivalent scores} / \text{chronological age} \times 100$
 - Example: $\frac{12 \text{ month developmental age equivalent score}}{24 \text{ months chronological age}} \times 100 = 50 DQ$

Raw scores are also mapped into growth scores, with a mean of 500 and a SD of 100 for each subtest. Growth scores provide an equal-interval scale by which progress can be measured over time.

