### 8.2 Demographic Data and Onset of Disease

A patient's date of birth, gender, gestational age, race and ethnicity will be recorded at Screening. If available, information on parity, any complications during pregnancy, delivery type, Apgar scores, placental condition, and history of *in utero* seizures will be recorded. Date of onset of signs and symptoms suggestive of MoCD will be recorded, as available.

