6.1.3.4. Prenatal and Antenatal History

The following prenatal and antenatal history, if available will be summarized:

- Gestational age (weeks)
- Any complications during pregnancy
- Delivery type
- Placental condition
- History of in utero seizures
- Apgar scores

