6.2.2.2. Developmental Assessments

Changes from baseline to post-treatment assessments in the Bayley-III will be summarized using descriptive statistics. The raw, scaled, age-equivalent, and DQ scores will be summarized for the Cognitive Scale and Fine Motor and Gross Motor subtests. Additionally, the composite score for cognitive and motor scales will be summarized for subjects up to 42 months in age or subjects with severe disability and the Bayley assessment is more appropriate. Language Scale results will be displayed in a by-subject data listing.

A summary of the frequency and percentage of subjects at each level of the 5-level classification system of the GMFCS-E&R will be presented by visit.

Changes from baseline to post-treatment assessments in the WPPSI will be summarized using descriptive statistics. A by-subject data listing of all WPPSI IV assessments will be produced.

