6.2.2.6. Growth Parameters

Body weight, length, head circumference, and body mass index (BMI) will be analyzed by converting each parameter to age-adjusted z-scores and age percentiles and descriptive statistics will be presented for each parameter, as well as, for the change from baseline. The 5th, 25th, 50th, 75th, 90th, and 95th percentiles will be calculated.

Weight, length, head circumference, and BMI data including age-adjusted z-scores and percentile for each growth parameter-for-age will be presented in a by-subject data listing.

In addition, the following individual subject's growth charts will be produced with a flag for start of ORGN001 infusion and will include a symbol representing dose changed, if applicable: weight-for-age percentiles, length-for-age percentiles, head circumference-for-age percentiles, and BMI-for-age percentiles.

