8. APPENDICES

8.3. Technical Specifications for Derived Variables

The following derived data will be calculated prior to analysis.

Age

Age will be presented as the number of days or months between date of birth and the reference date and will be calculated as follows:

Age in days: (Visit date – date of birth) + 1 day

Age in months: ((Visit date – date of birth) + 1 day)/30.4375

The following ages in [Table 3](#) may be computed, with reference dates indicated.

Table 3: Age and Reference Date

AGE	REFERENCE DATE
Age at study enrollment (months)	• Date of signing ICF
Age at first symptom (days)	• Date of first symptoms
Age at first ORGN001 infusion (days)	• Date of first infusion
Age at each developmental assessment (months)	• Date of developmental assessment

If the reference date is not complete, then age at reference date will be determined by the month and/or year of date of birth and reference date.

Weight and Height

Weight in pounds will be multiplied by 0.4536 to be converted to kilograms; and height in inches will be multiplied by 2.54 to be converted to centimeters.

The BMI will be calculated by dividing the subject's weight in kilograms by the subject's height in meters squared. The units are kg/m².

BQL and LLOQ Values for Clinical Laboratory Parameters

For all clinical laboratory parameters, values that are reported as below quantification level (BQL) or lower limit of quantification (LLOQ) will have numeric values set equal to the BQL or LLOQ lower limit (e.g., if BQL <2, then value will be set equal to 2). However, the original value will be displayed in by-subject data listings.

Date of Infusion

Date of first ORGN001 infusion, as well as date of last ORGN001 infusion will be derived.

Time from First Infusion to Applicable Assessments (Days)

For all applicable assessments, time on treatment from first infusion will be calculated as follows:

- If visit date is on or after first infusion = (Visit date – Day 1 Infusion date) + 1 day
- If visit date is prior to first infusion = (Visit date – Day 1 Infusion date)

Time from First Infusion to Applicable Assessment (Months)

For all applicable assessments, time on treatment from first infusion will be calculated as follows:

- If visit date is on or after Day 1 infusion = ((Visit date – Day 1 Infusion date) + 1 day)/30.4, rounded to 1 decimal place
- If visit date is prior to Day 1 infusion = (Visit date – Day 1 infusion date)/30.4, rounded to 1 decimal place

Time on Study (Days)

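### DQ is computed on chronological age although gestational age is recorded, so a child born early and enrolled young would have an upward-biased change from baseline

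*SAP*

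**What the plan says.** SAP 4.1.2 defines the developmental quotient: "The DQ is the age equivalent score divided by chronological age", times 100. SAP 8.3 gives the general rule: "Age will be presented as the number of days or months between date of birth and the reference date". Its Table 3 takes age at each developmental assessment from the assessment date and lists no gestation-corrected age.

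Gestational age is available. Protocol 8.2 says: "A patient's date of birth, gender, gestational age, race and ethnicity will be recorded at Screening". The only use the SAP states for it is a summary under prenatal and antenatal history (6.1.3.4).

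DQ is a reported efficacy result. SAP 6.2.2.2 summarizes changes from baseline in the Bayley-III and specifies: "The raw, scaled, age-equivalent, and DQ scores will be summarized for the Cognitive Scale and Fine Motor and Gross Motor subtests". In SAP 6.2.2.6 the growth parameters are "analyzed by converting each parameter to age-adjusted z-scores and age percentiles", again with change from baseline. Neither that section nor SAP 8.4 says which age enters the growth-chart macros.

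The study has no comparator (Protocol 1.6), no hypothesis test (SAP 6.2.1.4) and no sensitivity analysis (SAP 6.2.1.5). At least 4 patients will be enrolled (Protocol 13.2), and neither age nor gestation is an entry criterion (Protocol 4.2, 4.3).

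**The concern.** For a child born early, the weeks missed before term are a fixed amount inside a growing denominator. As the child ages, those weeks become a smaller share of chronological age, so DQ moves toward its corrected value even if development relative to corrected age does not change. A change from baseline in DQ then mixes this arithmetic drift with real development.

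With no control arm, nothing cancels the drift, and with about 4 children one affected child carries a large weight in the mean. Direction matters here. Protocol 1.6 expects clinical status to stay the same after the switch from rcPMP and would read that as comparable efficacy. An upward drift could therefore show a gain where there is none, or make a decline look smaller.

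**Working it through.** **The plan's own figure.** SAP 4.1.2 gives a 12-month age equivalent at 24 months chronological age: 12/24 × 100 = 50. This reproduces exactly.

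**Inputs.** The DQ formula is from SAP 4.1.2, the month length of 30.4375 days from SAP 8.3, and the 6-month initial period from the protocol synopsis. Term at 40 weeks, the gestational ages, the baseline ages and the developmental rates are assumptions, because the documents give none.

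**Model.** A child born w months early develops at a constant rate r on corrected age, so the age equivalent at chronological age A is r(A − w). Then:

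- DQ under the SAP = 100r(1 − w/A)
- 6-month change under the SAP = 100rw[1/A − 1/(A + 6)]
- DQ on corrected age = 100r at every visit, so its change is 0

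Eight weeks early gives w = 8 × 7/30.4375 = 1.84 months. Four weeks early gives w = 0.92.

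**Worked case** (8 weeks early, r = 1, baseline at 6 months): (6 − 1.84)/6 × 100 = 69.3, and (12 − 1.84)/12 × 100 = 84.7. The change is +15.3 from unrounded values.

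| Baseline age (months) | 4 weeks early, r = 1 | 8 weeks early, r = 1 | 8 weeks early, r = 0.5 |
|---|---|---|---|
| 6 | +7.7 | +15.3 | +7.7 |
| 12 | +2.6 | +5.1 | +2.6 |
| 24 | +0.8 | +1.5 | +0.8 |
| 36 | +0.4 | +0.7 | +0.4 |

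For a term birth w = 0, so every entry is 0.

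**Group mean.** If four children contribute a DQ and one was born 8 weeks early (r = 1), the mean change moves by 15.3/4 = 3.8 points from a 6-month baseline, 1.3 from 12 months and 0.2 from 36 months. At half rate from 12 months it moves by 2.6/4 = 0.6.

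**Longer follow-up.** Over an assumed 36 months of treatment, the same child (r = 1) drifts by +26.3 from a 6-month baseline, +11.5 from 12 months and +2.6 from 36 months.

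**Stalled development.** Suppose the age equivalent stays at 6 months from age 12 to 18 months, in a child born 8 weeks early.

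- Chronological age: 6/12 = 50.0 to 6/18 = 33.3, a change of −16.7
- Corrected age: 6/10.16 = 59.0 to 6/16.16 = 37.1, a change of −21.9

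DQ falls on both bases, but the SAP's version understates the fall by 5.3 points.

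**Direction in general.** Chronological-age DQ equals corrected-age DQ × (1 − w/A). The bias in change is therefore w × (corrected DQ at baseline/baseline age − corrected DQ at visit/visit age). It is positive unless corrected DQ itself grows by a larger factor than age does. From 6 to 12 months, that would require corrected DQ to more than double.

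**Growth z-scores.** The documents contain no growth reference tables, so no size can be derived.

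**The case against.** The strongest objection is that no affected patient is shown. No document says that any child was born early, and Protocol 1.4 says only that age at enrollment depends on who is already receiving rcPMP. SAP 4.1.4 says most subjects completed the WPPSI, which Protocol 9.4 gives from 3 years of age, and SAP 4.1.7 provides charts for children over 5. From a 36-month baseline the drift is under 1 point in 6 months at either prematurity tabulated. The disease description also makes normal-rate development a generous assumption. All of this stands and limits the size of the point. It does not settle baseline age: enrollment was expected from February 2014, the SAP cites a September 2018 drug dictionary, and the extension is open-ended, so a child enrolled in infancy could reach WPPSI age on study.

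A reader might go further and infer that preterm infants will automatically show catch-up that the trial credits to ORGN001. The documents do not support that. Catch-up requires continued progress, and a stalled child's DQ falls. The summaries are descriptive, stability is what the protocol expects, and raw and age-equivalent scores, which have no age divisor, are reported beside DQ.

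A reader might also infer that growth z-scores certainly use uncorrected age. That follows only from the general age definition and from silence in SAP 6.2.2.6 and 8.4. Table 3 names no age for growth measures.

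Parts of the SAP are redacted, including text after the missing-data rule for developmental assessments (6.2.1.1.1) and much of the appendices. A correction stated there cannot be excluded.

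By-subject listings would probably let a careful reader identify a preterm child among so few. They would not show that child's corrected DQ.

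**Conclusion.** The point holds in conditional form. The chronological-age denominator is explicit, gestational age is collected, and the readable plan contains no corrected-age analysis. For a child born early and enrolled young, the change in DQ is biased upward. For a child born 8 weeks early and developing steadily at the normal rate on corrected age, the 6-month bias is about 15 points from a 6-month baseline, 5 from 12 months, 1.5 from 24 months and 0.7 from 36 months. At half rate each figure halves, and at term it is zero. These figures rest on assumed gestational ages, baseline ages and rates, so they show what could happen and do not estimate what did. Whether any enrolled child is affected is unknown. For growth, the supportable statement is that the age basis is not given in the readable text and the bias cannot be sized. The point concerns a secondary efficacy summary and leaves the primary safety objective untouched.

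**What to change.** In SAP 4.1.2 and 8.3, for any child born preterm (with the cut-off stated, since the documents give none), add DQ computed on gestation-corrected age: chronological age minus (40 weeks minus gestational age). Use that age basis at baseline and at every later visit. Report it beside the chronological-age DQ, with gestational age in the same listing. In SAP 6.2.2.6 and 8.4, state which age enters the growth z-scores and give the corrected-age version for the same children.

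Do not stop the correction at 24 months. For a child born 8 weeks early (r = 1) with a 20-month baseline and a 26-month visit, switching basis would take DQ from 100 to (26 − 1.84)/26 × 100 = 92.9, a spurious fall of 7.1 points. The current SAP gives 90.8 to 92.9, or +2.1, so the switch would do more harm than the present rule.

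The cost is one extra derived variable and a second DQ column, plus the corrected z-scores for the same children, all from data already collected. If every child was born at term, no result changes.
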